If a patient withdraws prematurely for any reason after D3, the attributed randomization code and attributed IMD will not be reused nor will the patient be allowed to re-enter in the study afterwards.

V.6 - Intervention duration

Total duration of the intervention will be of approximately 15 weeks from initiation visit (V1) detailed in section VI.3 to end of study visit (V9) detailed in section VI.6 for patients randomised in the study investigational group.

For patients randomised in the control group, the total duration will be approximately 12 weeks from initiation visit (V1) detailed in section VI.3 to end of study visit (V9) detailed in section VI.6.

V.7 - OBSERVANCE/COMPLIANCE

All patients will receive appropriate training in the safe use of the automated insulin delivery system in both open and closed-loop features for investigational group, and training of CGM only for control group.

Patient ability to follow instructions for use of the automated insulin delivery system required by the protocol will be assessed by the investigator during the selection, initiation and run-in periods. The investigator reserves the right to withdraw patients who would not be able to follow the instructions.

Patients will then come back to their initial treatment. These patients will be replaced if the withdrawal occurs before D3.

Observance of patients during the follow-up period will be assessed by patient's family nurse, HHP and investigator, based on the quality of the glycaemic data and information provided by the patient in the patient's diary. Observance data will be collected in the e-CRF.

All patients will have regular contacts with the operational study team during the home study periods including 24/24 hours 7/7 days telephone support by home healthcare providers. In addition, a hotline 24/24h by the investigator center for medical support will be available.

V.8 - CONCOMITANT MEDICATIONS

Any initiation of medication that could interfere with the automated insulin delivery system or with insulin therapy **will not be authorized** during the course of the study. These medications include:

- Glinides,
- Sulfonylurea,
- Glucocorticoids* (*with the exception of patients treated with stable prednisone < at 10 mg equivalent per day since 3 months)
- Or any other medication that could interfere with glycaemic levels.

Authorized glycaemic control concomitant treatments are:

- -Metformin, DDP4 inhibitors, GLP1-receptor agonists.
- -First aid kit

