Each secondary efficacy endpoint will be summarised at each time point using descriptive statistics and compared between study groups using Cochran-Mantel-Haenszel chi-squared tests adjusted on the HbA1c level at baseline (2-categories stratification variable) or analyses of covariance with or without repeated measures (depending on the analysed parameter and its frequency of collection in both study groups) adjusted on the HbA1c level at baseline.

When appropriate, analyses based on CGM measures will be performed considering (1) the full 24-h day, (2) diurnal period (from 06.00 H to 23.59 H) and (3) nocturnal period (from 00.00 H to 05.59 H) separately.

When relevant, continuous, longitudinal endpoint data (e.g. HbA1c, Total daily insulin dose, body weight) will be analysed using the mixed effects model for repeated measures method based on the restricted maximum

likelihood for estimation with several prespecified fixed effects, including first-order interactions with time, and the corresponding endpoint as the dependent variable in the model. ANCOVA will be used for analyses of measures taken at a single time point post baseline in both study groups.

X.3.5 - SAFETY EVALUATION

Safety data will be tabulated descriptively by study group and assessment time, when relevant. Extent of exposure and Adverse Events will be tabulated in the Randomised ITT and the safety data sets (defined in section X.2.1). No statistical test will be performed.

X.3.5.1 - EXTENT OF EXPOSURE

Duration of the 4 study periods (Selection, Initiation, Run-in and Follow-up periods) and overall study duration will be tabulated (expressed in days) by study group (and globally), as both quantitative and categorical data.

Overall study duration is defined as the time interval between the actual date of the selection visit (*VO included*) and the actual date of the end of study visit (*V9 excluded*) whether the end of study occurred at the time of premature withdrawal or on visit date corresponding to D90 as planned, i.e., as the time interval equal to "date of end of study visit (V9) - date of selection visit (V0)".

X.3.5.2 - ADVERSE EVENTS (AES)

The time period for the recording of Adverse Events (AEs) is the time interval between selection (V0) and end of study (V9) divided in 2 periods, either before or after the initiation visit (V1). All reported AEs will be classified in one of these 2 periods, according to their start date.

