AEs tabulated evaluations described below will be performed on Study Emergent Adverse Events (SEAEs). AEs occurring before the initiation visit (V1) will be tabulated in the Randomised ITT and the safety data sets separately, if relevant, or they will be listed if too few patients are concerned.

Each AE (whether serious or not serious, according to their regulatory definition provided in section VIII.1) having been reported throughout the study for a given patient will be classified by Preferred Term (PT) and corresponding primary System Organ Class (SOC), using the MedDRA terminology, prior to the study database lock.

An AE will be categorised as Study Emergent if it begins at the earliest on the day of the initiation visit (V1). In case of missing or partial AE start date, an AE will be considered as Study Emergent (SE):

- (1) if the AE start date is unknown,
- or (2) if the partial AE start date is on or after the date of the initiation visit (V1) (i.e., 'year' or 'year and month' is/are 'the same as' or 'after' those of the date of Visit 1).

An overall summary of AEs will be provided by study group, including:

- the number and percentage of patients with at least 1 AE and the total number of AEs,
- the number and percentage of patients with at least 1 SEAE and the total number of SEAEs,
- the distribution of the number of SEAEs reported by patient (in 5 categories, if relevant: 1 SEAE, [2 3] SEAEs, [4 6] SEAEs, [7 9] SEAEs or 10 or more SEAEs),
- the number and percentage of patients with at least 1 Serious SEAE and the total number of Serious SEAEs,

- the number and percentage of patients with at least 1 possibly IMD related SEAE (possibly IMD related SEAEs being defined as SEAEs for which the investigator has reported at least once either 'Causal relationship' or 'Probable' or 'Possible' for the relationship to the IMD) and the total number of those possibly IMD related SEAEs,
- the number and percentage of patients with at least 1 SEAE possibly related to investigation procedures (SEAEs possibly related to investigation procedures being defined as SEAEs for which the investigator has reported at least once either 'Causal relationship' or 'Probable' or 'Possible' for the relationship to the investigation procedures) and the total number of those SEAEs possibly related to investigation procedures,
- the number and percentage of patients with at least 1 AE leading to study premature withdrawal and the total number of those significant AEs.

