This summary table will also be provided for Serious Adverse Events (SAEs) separately.

The number and percentage of patients with at least 1 SEAE will be tabulated by study group, System Organ Class (SOC) and Preferred Term (PT) on the safety data set, as well as:

- the number and percentage of patients with at least 1 most common SEAE (defined as those occurring in at least 5.0% of the patients from the safety data set), if it appears to be relevant,
- the number and percentage of patients with at least 1 SEAE by most severe intensity,
- the number and percentage of patients with at least 1 SEAE by worst recorded relationship to the IMD,
- the number and percentage of patients with at least 1 SEAE by worst recorded relationship to investigation procedures.

The number and percentage of patients with at least 1 SEAE will also be tabulated by study group and SOC only on the safety data set.

For the overall evaluation of AEs (including counting of the number of AEs reported), recurring AEs (i.e., AEs classified under the same Preferred Term (PT)) for a given patient in a given period will be counted only once for the patient concerned in the period concerned.

If relevant, the number and percentage of patients with at least 1 SAE will be tabulated by study group, System Organ Class (SOC) and Preferred Term (PT), separately from all AEs, in a second step.

Moreover, SEAEs occurring during the Run-in period (which only concerns patients allocated to the investigational group) will be tabulated in the safety data set separately, if relevant, or they will be listed if too few patients are concerned.

All SAEs reported throughout the study (i.e., from the date of the selection visit (VO) onwards), all AEs leading to study premature withdrawal (which constitute significant AEs) and deaths if applicable will be listed separately by study group. They will be exhaustively described on an individual basis, including all reported information in the section devoted to AEs in the e-CRF, as well as their start date (i.e., both (1) the time interval between the date of the selection visit (VO) and the occurrence of the AE and (2) the timing of onset of the AE in relation to DO), and duration of the AE.

Adverse Device Effects and Device Deficiencies will be listed separately and they will be exhaustively described on an individual basis, in a similar manner to SAEs, if relevant.

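### The AE summary counts a repeated Preferred Term once per patient and period even in its event totals, so those totals understate events and can distort the arm comparison in either direction

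*Combined protocol and SAP*

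**What the plan says.** Section X.3.5.2 sets out an overall AE summary by study group. Most rows pair a patient count with an event count, for example "the number and percentage of patients with at least 1 SEAE and the total number of SEAEs". The same pairing is used for all AEs, serious SEAEs, SEAEs possibly related to the device, SEAEs possibly related to investigation procedures, and AEs leading to withdrawal. One further row gives "the distribution of the number of SEAEs reported by patient", in the categories 1, 2-3, 4-6, 7-9 and 10 or more. The table is repeated for SAEs.

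Later in the section comes the counting rule: "For the overall evaluation of AEs (including counting of the number of AEs reported), recurring AEs", meaning AEs under one Preferred Term (PT) in the same patient and period, "will be counted only once for the patient concerned in the period concerned".

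The opening of X.3.5.2 divides the recording interval (V0 to V9) into two periods, before and after V1, and assigns every AE to one of them by start date. Section X.3.5 makes safety descriptive: "No statistical test will be performed".

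**The concern.** Once-only counting is the normal convention for the number of patients with an event. Here the parenthesis in the rule extends it to the number of events. Because all time after V1 is a single period, a patient with ten reports of one PT after V1 adds 1 to the total of SEAEs and falls in the category for 1 SEAE. The rows are labelled as event counts, but they would hold counts of distinct patient-PT pairs.

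Recurrence is plausible in this trial. The infusion set is changed every 3 days (section V.1.1). Over about 15 weeks in the investigational group (section V.6) that is 15 × 7 / 3 = 35 changes per patient, each an occasion for a repeat of the same site event. This shows opportunity for recurrence, not a rate. As safety is untested, the descriptive counts are what the reader has to judge by.

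**Working it through.** **1. What the rows become.** Let Y be the number of events of one PT in one patient after V1. The label promises the sum of Y. The rule delivers the sum of min(Y, 1). The cap is one per patient per PT per period, so different PTs still add up. With no recurrence the two sums are equal. With any recurrence the second is smaller.

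**2. Arm size, from section X.1.** Inputs are a difference of 17, SD 16, two-sided 5% and 90% power. Then n = 2 × (16/17)² × (1.960 + 1.282)² = 18.6, rounded up to 19. Next, 19 × 1.10 = 20.9, rounded up to 21, and 21 / 0.75 = 28. The plan's 28 per group reproduces and is not in dispute. It serves only as the arm size below; the percentages and ratios do not depend on it.

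**3. Similar clustering in both arms.** The recurrence rates are assumptions, since the documents give none. For a Poisson mean λ per patient and one PT, the full count is 28λ and the count under the rule is 28(1 − e^(−λ)). The true ratio is 2 throughout.

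| Assumed λ, two arms | All events | Under the rule | Kept | Apparent ratio |
|---|---|---|---|---|
| 0.1 v 0.05 | 2.8 v 1.4 | 2.66 v 1.37 | 95.2% v 97.5% | 1.95 |
| 0.5 v 0.25 | 14 v 7 | 11.0 v 6.2 | 78.7% v 88.5% | 1.78 |
| 1 v 0.5 | 28 v 14 | 17.7 v 11.0 | 63.2% v 78.7% | 1.61 |
| 2 v 1 | 56 v 28 | 24.2 v 17.7 | 43.2% v 63.2% | 1.37 |
| 4 v 2 | 112 v 56 | 27.5 v 24.2 | 24.5% v 43.2% | 1.14 |

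No PT can contribute more than 28 to an arm's total after V1.

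**4. Unequal clustering.** For a gamma-Poisson count with mean m and shape k (small k means events concentrated in few patients), the count under the rule is 28(1 − (1 + m/k)^(−k)). The values of m and k are again assumptions.

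- Mean 1 in both arms, k = 10 v 0.25: all events 28 v 28, difference 0. Under the rule 17.2 v 9.3, difference 7.9.
- Mean 2 (k = 0.2) v mean 1 (k = 5): all events 56 v 28, difference +28. Under the rule 10.7 v 16.8, difference −6.1.

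A difference can therefore appear from nothing, or change sign.

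**5. Follow-up time.** Section V.6 gives about 15 weeks from V1 to V9 in the investigational group and about 12 in the control group. At equal weekly rates, full event counts have ratio 15/12 = 1.25 from exposure alone. Under the rule that ratio is 1.215 at an assumed 0.02 events per week and 1.017 at 0.3. Complete counts therefore need person-time beside them.

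**The case against.** The strongest reply is that much of what matters is kept elsewhere.

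- Section VII.3.1 has separate counts of hypoglycaemic events (overall, diurnal, nocturnal, severe, third-party-assisted, hospitalised) and of severe hyperglycaemic events.
- X.3.5.2 tabulates hospitalisations per patient and lists SAEs, withdrawal AEs and, if relevant, adverse device effects and device deficiencies one by one. A site reaction judged device-related would appear in those listings.
- The rule is disclosed, applies alike to both arms and feeds no test.

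This stands as a limit on the harm but does not cure it. Listings give no totals by arm. Repeated non-serious AEs not judged device-related have no other event-level tabulation. Most glycaemic counts are defined on CGM readings (section VI.7.1.9), and control patients wear no sensor between its removal at V1 (section VI.3.1) and the new one at day 70 (section VI.5.3). Over that stretch, reported AEs are the main record of their recurrent glycaemic events.

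A second reply is that the period in the rule might mean the four study periods of section X.3.5.1. The opening of X.3.5.2 points to its own two periods. Even on the other reading, the whole follow-up period would be one unit.

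A third is that relabelling the rows as distinct PTs per patient would remove the mislabelling. It would, but the event totals would still be missing.

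A reader might also infer that the rule always shrinks differences between the arms. The documents do not support that: it requires similar clustering in both arms, and step 4 of the working shows the contrast growing from zero or reversing. Nor does the rule cap a patient at one event overall, or remove recurrent device risks from the report altogether.

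**Conclusion.** The point holds as a counting defect in the descriptive AE summary. The text of X.3.5.2 is explicit, so it does not rest on assumed rates that the total-number rows and the SEAE distribution would hold patient-PT pairs and fall short of the event count whenever a term recurs.

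The size does rest on assumptions. For Poisson rates of 0.05 to 4 per patient per PT, between 97.5% and 24.5% of events are kept, so the loss runs from negligible to large. A true ratio of 2 appears as 1.95 down to 1.14 with similar clustering; with unequal clustering neither size nor direction can be fixed in advance. No planned estimate or test changes. What is at stake is whether the safety tables report what their labels say, and the change should be made before the SAP is final.

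**What to change.** Amend the counting sentence in X.3.5.2, and carry it into the SAP, as follows:

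- Recurring AEs under one PT are counted once per patient and period for numbers and percentages of patients only.
- Every reported event is counted in all total-number rows (AEs, SEAEs, serious, device-related, procedure-related, withdrawal, and the SAE version of the table) and in the per-patient SEAE distribution.
- Each total after V1 is shown by arm with events per patient-time from V1 to end of study, so that the 15 versus 12 week difference is not read as an effect.

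If the sponsor also wants the distinct-term count, it can stay as an additional row labelled as such.

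The cost is a sentence or two of text plus table programming. No new data are needed: section VIII.2.1 already has every AE entered in the e-CRF. Under section X.3 the SAP is approved only after the Data Review Meeting, and section X.5 provides for documenting the change.

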- Number of severe nocturnal hypoglycaemic events (i.e., occurring from 00.00 H to 05.59 H)
- Number of severe hypoglycaemic events requiring third party assistance
- Number of severe hypoglycaemic events requiring hospitalization
- Number of severe hyperglycaemic events (≥ 300 mg/dL for over 1 hour).

[figure not shown]
Adverse events and device deficiencies/failure will be collected from the signature of the informed consent to study end.

A Data Safety Monitoring Board (DSMB) will review the safety data of the five first patients of each group, then 25 patients having completed the study, and more frequently if judged necessary by the DSMB.

Composition, role and frequency of DSMB meetings will be detailed in the separate DSMB Charter.

VII.3.2 -

VIII - SAFETY AND DEVICE DEFICIENCIES

VIII.1 - DEFINITIONS

Adverse Event (AE)

Any untoward medical occurrence, unintended disease or injury, or untoward clinical signs (including clinically significant abnormal laboratory findings) in patients, users or other persons, whether or not related to the investigational medical device.

This definition includes events related to the procedures involved (see definition below).

For users or other persons, this definition is restricted to events related to investigational medical devices.

Investigation Procedure

Any procedure specific to the clinical investigation. All activities related to the use of a medical device may be considered investigation procedures.

Note: "Preceding investigation procedure" shall be understood as a procedure which is imposed by the Clinical Investigation Plan and which has taken place before (or coincided in time) with the serious adverse event.

Adverse Device Effect (ADE)

Adverse Event related to the use of an investigational medical device.

This definition includes adverse events resulting from insufficient or inadequate instructions for use, deployment, implantation, installation, or operation, or any malfunction of the investigational medical device.

This definition includes any event resulting from use error or from intentional misuse of the investigational medical device.

Abnormal laboratory value

All abnormal laboratory values that the investigator is aware of will be reported as Adverse Events if the investigator categorizes their values as « Clinically Significant » (CS).

Serious Adverse Device Effect (SADE)

Adverse Device Effect that has resulted in any of the consequences characteristic of a Serious Adverse Event.

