The primary analysis of the primary efficacy endpoint is detailed in section X.3.3. All other efficacy and safety statistical results provided will be exploratory and exclusively descriptive. They may not lead to any causal interpretation. As a consequence, the statistical significance level of the various two-sided tests performed will be 5.0%. No adjustment for multiplicity will be made.

Gaussian quantitative variables will be analysed using parametric ANCOVA model and HbA1c category level at baseline as a cofactor.

Non-gaussian quantitative variables and ordinal qualitative variables will be analysed using a non-parametric ANCOVA model and HbA1c category level at baseline as a cofactor (performed on ranks).

Depending on the analysed parameter and its frequency of collection in both study groups, ANCOVA will be performed with or without repeated measures.

Nominal qualitative variables will be analysed using Cochran-Mantel-Haenszel (CMH) chi-squared tests.

X.3.2 - DEMOGRAPHIC AND OTHER BASELINE CHARACTERISTICS

Demographic and other baseline characteristics recorded up to D0 will be tabulated by study group (and IMD actually equipped with) and overall in the safety data set. No systematic statistical test will be performed to compare both groups at baseline.

Comorbidities, as well as medical and surgical history separately at selection will be summarised by study group and overall using the MedDRA codes of System Organ Classes (SOC) and Preferred Terms (PT).

Clinical laboratory evaluation at selection and Visit 1 separately will be summarised by study group and overall as both quantitative parameters (raw values converted in international units, if necessary) and qualitative parameters (relative positions regarding normal ranges in use in each laboratory involved).

All concomitant treatments with start date at the latest on the day before the initiation visit will be tabulated descriptively by study group and overall using the WHO_DRUG dictionary and the Anatomical Therapeutic Chemical (ATC) classification. Three (3) tables will be provided:

- one table showing the number and percentage of patients with at least 1 concomitant treatment with start date at the latest on the day before the initiation visit, by therapeutic area (ATC1 code corresponding to ATC system main group),
- one table by both ATC1 code and ATC system subgroup (ATC2 code),

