Unplanned hospitalisations whatever their reason (which will be reported as SAEs) will also be listed separately from all SAEs and they will be tabulated by study group, including the number and percentage of patients

hospitalised at least once during their study participation and the number of hospitalisations per patient (as both quantitative and categorical data).

X.3.5.3 - CLINICAL LABORATORY EVALUATION

In the safety data set, for each laboratory parameter (apart from HbA1c which is part of the secondary efficacy endpoints described in section X.3.4), laboratory results and their absolute variations from baseline (i.e., initiation visit (V1)) will be summarised as quantitative parameters using descriptive statistics by study group at the end of study visit (V9) planned to be performed at D90, using the observed case approach.

Number and percentage of patients above, below or within normal ranges in use in each laboratory involved will also be tabulated by study group for each parameter at study end.

A shift table will also be provided for each parameter at study end to depict the number and percentage of patients with post_baseline decreased laboratory values (from Within Normal Ranges to Below, from Above normal ranges to Within Normal Ranges or from Above normal ranges to Below), the number and percentage of subjects without changes (either always Within Normal Ranges or Above or Below) and the number and percentage of patients with post_baseline increased laboratory values (from Below to Within Normal Ranges, from Within Normal Ranges to Above or from Below normal ranges to Above) by study group.

X.3.5.4 - VITAL SIGNS, PHYSICAL FINDINGS AND OTHER OBSERVATIONS RELATED TO SAFETY

For systolic and diastolic resting blood pressure separately, quantitative descriptive statistics will be tabulated on the safety data set by visit planned and study group, using the observed case approach.

For each parameter separately, the absolute variations "post-initiation period – baseline (recorded at initiation visit (V1))" will also be tabulated by visit planned and study group.

[figure not shown]
X.3.5.5 - **CONCOMITANT TREATMENTS**

All concomitant treatments with start date at the earliest on the day of the initiation visit will be tabulated descriptively by study group in the safety data set using the WHO_DRUG dictionary and the Anatomical Therapeutic Chemical (ATC) classification. Three (3) tables will be provided:

[figure not shown]

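### The laboratory shift table groups patients by direction of movement only, so for parameters that can be abnormal in both directions it does not give the number of new low or new high values

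*Combined protocol and SAP*

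**What the plan says.** Section X.3.5.3 (Clinical laboratory evaluation) applies to every laboratory parameter except HbA1c and uses the safety data set. Its shift table at study end has three categories:

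- Decreased: "decreased laboratory values (from Within Normal Ranges to Below, from Above normal ranges to Within Normal Ranges or from Above normal ranges to Below".
- No change: "without changes (either always Within Normal Ranges or Above or Below".
- Increased: "increased laboratory values (from Below to Within Normal Ranges, from Within Normal Ranges to Above or from Below normal ranges to Above".

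The section does not ask for the individual transitions to be shown separately.

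Four other laboratory outputs bear on the point:

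- Range position at study end (X.3.5.3): "Number and percentage of patients above, below or within normal ranges in use in each laboratory involved will also be tabulated by study group".
- Range position at selection and at V1, by group (X.3.2): laboratory results are also summarised as "qualitative parameters (relative positions regarding normal ranges in use in each laboratory involved".
- Values and changes (X.3.5.3): "laboratory results and their absolute variations from baseline (i.e., initiation visit (V1)) will be summarised as quantitative parameters using descriptive statistics by study group".
- Adverse events (VIII.1): "All abnormal laboratory values that the investigator is aware of will be reported as Adverse Events", provided the investigator judges them clinically significant.

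Section X.3.5 says that safety data are tabulated descriptively, without tests.

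**The concern.** A laboratory shift table exists mainly to show how many patients left the normal range during treatment, in which direction, and whether this differs between arms. Here nine possible transitions are reduced to three counts by direction of movement. Each count mixes patients who end within range with patients who end outside it. A fall from high to normal is counted with a new low value, and a rise from low to normal with a new high value. Equal percentages in the two arms could therefore reflect different patterns. With no safety test planned, a reader comparing the arms depends on what the descriptive tables can show.

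**Working it through.** The plan gives no figure for this table, so there is none to reproduce. The check is whether the planned outputs determine the numbers of new low and new high values.

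**Inputs.** Category definitions and V9 range positions are from X.3.5.3, V1 range positions from X.3.2, and 28 randomised patients per group from X.1. The last is only the size of the illustration. Write B, W and A for below, within and above range, with V1 first and V9 second.

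**1. Map the cells.**
- Decreased = WB + AW + AB
- No change = BB + WW + AA
- Increased = BW + WA + BA
- New low = WB + AB
- New high = WA + BA

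Each planned count holds one cell ending within range and two ending outside it.

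**2. The three counts alone.** Take 28 patients with 6 decreased, 16 unchanged and 6 increased.
- If the decreases are all AW and the increases all BW, new abnormalities = 0.
- If they are all WB and all WA, new abnormalities = 6 + 6 = 12.
- The 16 unchanged patients may include anything from 0 to 16 who are persistently abnormal.

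**3. Add the V1 and V9 range positions.** The counts give 3 independent equations and the two sets of range positions give 5. They share the group total, so together they give 3 + 5 − 1 = 7 equations for 9 cells. Adding new low, or new high, as a further row raises the rank from 7 to 8, so neither can be calculated from the planned outputs in general. With positions of 6/16/6 (below/within/above) at both visits and shift counts of 6/16/6, total new abnormalities can still lie anywhere from 6 to 12.

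**4. Two arms that print identically**, with nobody crossing the whole range:

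| Transition | Arm X | Arm Y |
|---|---|---|
| WB | 6 | 0 |
| BW | 6 | 0 |
| WA | 0 | 6 |
| AW | 0 | 6 |
| WW | 10 | 10 |
| BB | 0 | 6 |
| AA | 6 | 0 |
| Total | 28 | 28 |

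| Output | Arm X | Arm Y |
|---|---|---|
| V1 below / within / above | 6 / 16 / 6 | 6 / 16 / 6 |
| V9 below / within / above | 6 / 16 / 6 | 6 / 16 / 6 |
| Decreased / unchanged / increased | 6 / 16 / 6 | 6 / 16 / 6 |
| New low (not printed) | 6 (21.4%) | 0 |
| New high (not printed) | 0 | 6 (21.4%) |

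Here 6/28 = 21.4%. All planned categorical outputs agree, while the new abnormalities lie on opposite sides.

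**5. Where the range positions or the counts suffice.**
- With shift counts of 6/16/6, going from 6/16/6 at V1 to 0/28/0 at V9 forces 0 new abnormalities.
- With the same shift counts, going from 0/28/0 to 6/16/6 forces 12.
- If nobody is below range at either visit, only WW, WA, AW and AA remain. Increased is then exactly WA (new high) and decreased exactly AW (return to normal).

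**The case against.** The strongest reply is that this table is not the only laboratory output. Range positions are tabulated at V1 and V9, changes from V1 are summarised, and clinically significant abnormal values become adverse events, tabulated under X.3.5.2. For creatinine, AST, ALT and gamma GT, where the concern is mainly upward, new highs and returns from high fall in opposite categories, and only a rise from below to within range blurs the increased count. The text also names each transition, so a programmer could print them. X.3 leaves the SAP to be approved after the data review meeting.

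Much of this stands. A reader might infer that the three counts can never show laboratory harm, or that new abnormalities appear nowhere in the planned output. The documents do not support either. The counts work where one side of the range is empty, some patterns can be read from the V1 and V9 positions, and the quantitative and adverse-event routes remain.

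The reply does not remove the point for two-sided parameters:

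- Step 4 already includes both range-position tables, and the arms still print alike.
- The V9 summaries use observed cases, so the V1 and V9 tables may cover different patients, which weakens any back-calculation.
- Summaries of change do not count patients leaving the range.
- The adverse-event route covers only values the investigator knows of and judges clinically significant, in an open-label trial (section III).
- Naming the transitions as parts of three groups is not an instruction to show them separately.

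**Conclusion.** The point holds within limits. As specified, the shift table does not give the number of new low or new high values for parameters that can be abnormal in both directions, and the V1 and V9 range-position tables do not recover it in general. In the illustration, a difference of 6 against 0 out of 28 on each side of the range is invisible in every planned categorical output.

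This rests on two assumptions. The 28 per arm is the planned randomised number; the safety set, and the patients with both values, may be fewer. The cell counts are invented to show that the outputs can coincide, and are not a forecast. The documents give no normal ranges or baseline distributions, so how often this would matter for a given parameter cannot be stated.

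The consequence is minor. One descriptive safety table is affected; the sample size, the primary analysis and the rest of the laboratory safety assessment are not.

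**What to change.** In X.3.5.3, and in the SAP table shell, replace the three pooled categories by the full 3x3 table of V1 position (below, within, above) against V9 position, per parameter and study group. Use patients with both a V1 and a V9 value as the denominator, and print that number. Add two summary rows:

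- New low: within or above at V1, below at V9.
- New high: within or below at V1, above at V9.

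The cost is a changed table shell and its program, with nine cells in place of three for each parameter. The data are already collected. The SAP is still to be approved after the data review meeting, and X.5 provides for recording such a change and its reason.
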